5 STUDY ACTIVITIES

5.1 Eligibility Criteria

Study Entry Criteria

For both Arms A and B; the eligibility criteria are that a subject has enrolled, participated in, and received at least 1 dose of rovalpituzumab tesirine in a parent study.

Arm A Optional Retreatment Criteria

Additional eligibility criterion for Arm A is that subjects who discontinued the study drug in the parent study have completed the treatment emergent AE reporting window (e.g., 30 days post last dose for Study SCRX001-002).

Subjects who elect optional retreatment in Arm A must meet all of the following eligibility criteria before receiving rovalpituzumab tesirine retreatment. Prior to providing retreatment to subjects, study investigators should consult with the AbbVie Medical Monitor.

Demographic and Laboratory Assessments

- 1. Tolerated their initial 2 doses of rovalpituzumab tesirine
- 2. Achieved clinical benefit from rovalpituzumab tesirine, defined as stable disease or better, and is determined that the subject would potentially benefit from additional treatment

Achieved clinical benefit as defined by stable disease or better and experienced radiographic disease progression at least 12 weeks after last dose of rovalpituzumab tesirine per RECIST 1.1

- 3. Received no other systemic anti-cancer therapy after rovalpituzumab tesirine treatment
- 4. Eastern Cooperative Oncology Group (ECOG) performance status of 0 or 1. See the Operations Manual, Appendix B for conversion of performance status using Karnofsky scales, if applicable
- 5. Minimum life expectancy of at least 12 weeks

- 6. Laboratory values meeting the following criteria within the screening period prior to the first dose of study drug:
 - Absolute neutrophil count (ANC) ≥ 1,500/μL;
 - Platelet count ≥ 75,000/μL;
 - Hemoglobin ≥ 8.0 g/dL;
 - Serum total bilirubin $\leq 1.5 \times$ upper limit of normal (ULN) or $\leq 3 \times$ ULN for subjects with Gilbert's disease;
 - Serum alanine aminotransferase (ALT) and aspartate aminotransferase (AST) ≤ 2.5 × ULN (≤ 5 × ULN if evidence of hepatic involvement by malignant disease);
 - Serum creatinine ≤ 1.5 × ULN or estimated glomerular filtration rate (eGFR)
 ≥ 30 mL/min/1.73 m² as calculated by the 4-variable Modification of Diet in Renal Disease study equation (GFR (mL/min/1.73 m²) = 175 × (serum creatinine [mg/dL])-1.154 × (age [years])-0.203 × 0.742 (if female) × 1.212 (if African American).³

Disease Activity

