2.2 Arm A Retreatment Visit Activities

Subjects in Arm A who elect retreatment will undergo the same schedule of assessments as the subjects in Arm B (Section 2.3), beginning with Day –1. Subjects from Arm A can receive treatment for no more than 2 cycles during each retreatment period with Cycle 1 starting on Day –1 and continuing through the Post-Cycle Response Assessment Visit (see Arm B, Section 2.3).

p. 6 of 31

The following assessments/activities should be completed ≤ 7 days before each retreatment period.

Activities are grouped by category (Interview, Exam, etc.). Further information about each activity is provided in Section 3.

ADDITIONAL RETREATMENT SCREENING: ≤ 7 DAYS BEFORE INITIATION OF RETREATMENT

□ INTERVIEW	 Meets eligibility criteria criteria for retreatment^a Adverse events Concomitant medications 	 ECOG status (0 – 1 required for retreatment)
* EXAMS	Physical exam	Vital signs
5 LOCAL LABS & IMAGING	 Pregnancy test (urine) Disease/response assessment^b 	 Echocardiogram
CENTRAL LABS	Complete blood countChemistries	Coagulation testsUrinalysis

ECOG = Eastern Cooperative Oncology Group

- a. Eligibility criteria are provided in the Protocol, Section 5.1.
- b. Response assessment and brain MRI (if clinically indicated) to be performed only in subjects who have not yet experienced radiographic disease progression.

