□ INTERVIEW	 Adverse events Concomitant medications Fluid retention questionnaire (see example in Appendix C)^a 				
EXAMS	Vital signs Physical exam				
∠ CENTRAL LABS	Complete blood count Urinalysis Chemistries				
subject and NOTES: Every third	a. Fluid retention questionnaires need to be collected from and discussed with the subject and new questionnaires provided to the subject.				
Fluid retention questionnaire follow-up phone call					
TREATMENT CYCLE: DAY 29 ± 3 DAYS					
Adverse events Fluid retention questionnaire (see example in Appendix C) ^a Concomitant medications					
* EXAMS	Physical exam Vital signs				
▲ CENTRAL LABS	Complete blood count Urinalysis Chemistries				
 a. Fluid retention questionnaires need to be collected from and discussed with the subject and a new questionnaire provided to the subject. NOTES: Every third cycle excludes rovalpituzumab tesirine and dexamethasone treatment. 					

TREATMENT	CYCLE:	DAY	36 + 2	Day	/S
------------------	--------	-----	--------	-----	----

□ INTERVIEW •	Fluid retention questionnaire follow-up phone call
---------------	--

POST-CYCLE RESPONSE ASSESSMENT: WITHIN 7 DAYS OF NEXT DOSE OF STUDY DRUG:

□ INTERVIEW	•	Fluid retention questionnaire (see example in Appendix C) ^a	•	Adverse events Concomitant medications
* EXAMS	10	Physical exam		
5 LOCAL LABS & IMAGING	•	Disease/response assessment ^b		

- a. Fluid retention questionnaires need to be collected from and discussed with the subject and new questionnaires provided to the subject.
- b. Response assessment and brain MRI (if clinically indicated) to be performed only in subjects who have not yet experienced radiographic disease progression.
- NOTE: This appointment is conducted at a clinic visit on Days 35 42 of each cycle and is to be conducted if the subject is continuing with royalpituzumab tesirine treatment.

END OF TREATMENT: 42 DAYS ± 3 DAYS AFTER LAST DOSE (IF SUBJECT IS STOPPING TREATMENT)

□ INTERVIEW	 Fluid retention questionnaire (see example in Appendix C)^a 	Adverse eventsConcomitant medications
* EXAM	 Physical examination 	 Vital signs
5 LOCAL LABS & IMAGING	Pregnancy test (urine)	 Disease/response assessment^b
A CENTRAL LAB	Complete blood countChemistries	Coagulation testsUrinalysis

- a. Fluid retention questionnaires need to be collected from and discussed with the subject.

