3.9 Other Assessments

All assessments take place as described in Section 2.

Eastern Cooperative Oncology Group (ECOG) scale will be used to assess performance status at the Screening visits in Arm A retreatment and Arm B. For conversion of performance status using Karnofsky scales to ECOG, see Appendix B.

MRI of the brain (if clinically indicated) should be performed to confirm absence of active central nervous system (CNS) tumor or metastases. Brain MRI may be substituted by computerized tomography (CT) with IV contrast at the discretion of the investigator if MRI testing is clinically contraindicated, not available, or if the subject is unable to tolerate MRI. MRI assessments will be performed at study visits as specified in Section 2.

CT imaging of the chest, abdomen, and pelvis, and neck (if indicated) as well as other relevant imaging, as described via RECIST v1.1, will be used for disease/response assessment. Assessment of response and progression will be determined by the investigator according to RECIST v1.1. These assessments will be conducted at study visits as specified in Section 2. Upon disease progression or initiation of new anticancer therapy, disease/response assessment will consist of subsequent anticancer therapies and dates, date of progression (if not already captured), and survival status. No subsequent radiography is required once disease progression has occurred.

Ongoing concomitant therapies (from subject's parent study) should be recorded at study visits as specified in Section 2 and will include the names of all concomitant medications, blood products, procedures, and radiotherapy, including dates of administration, dose regimen, route of administration, and purpose.

Subjects enrolled in Arm B or Arm A Retreatment will complete fluid retention questionnaires starting on Day 1 through the EOT Visit (refer to Section 2). Subjects will record their daily weights or new edema or dyspnea on the fluid retention questionnaire (Appendix C). Fluid retention questionnaires will be distributed to subjects on Day 1, Day 15, Day 29, and the Post-Cycle Response Assessment Visit. Each questionnaire records up to 7 days of daily weights and subjects should be provided with enough questionnaires to record their daily weight until their next on-site clinic visit.

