4.4 Toxicity Management

Standard supportive care for drug-related toxicity is permitted, including growth factors and blood product transfusions per local institutional standards. Other standard supportive care for symptom control or drug-related toxicity is allowed, such as analgesics, anti-emetics, electrolyte replacement, and hydration. Bone modifying agents for bone metastases are also permitted per local institutional standards. Other prescribed medications for non-neoplastic conditions are allowed, as well as vitamins and nutritional supplements.

Routine prophylaxis with vaccines is permitted; however, vaccines used should not contain live microorganisms.

If the subject is taking chronic suppressive anti-infectives (antiviral, antifungal, or antibacterial), appropriate investigation must be completed prior to enrollment, and documentation must exclude active infection. The subject should continue suppressive anti-infectives for the duration of study participation.

If a subject requires palliative radiation during the study (e.g., symptomatic worsening of a bone lesion) diagnostic imaging has to be performed to assess for radiographic progression prior to radiation, and documentation of non-progressive status by radiography will be captured in the eCRF. Any cancerdirected therapy a subject receives due to disease improvement should be discussed with the Therapeutic Area Medical Director in advance, if possible.

In the event of isolated central nervous system (CNS)-only progression during study treatment, investigational product may be withheld while local treatment is administered (e.g., radiotherapy) in accordance with institutional practice. Investigational product may be restarted 1 week after the completion of local CNS disease-directed therapy. If more than 6 weeks have elapsed since the previous dose of study drug, the subject should undergo a radiographic tumor assessment. If additional sites of progressive disease are present, the subject will be required to discontinue study drug, but may be eligible for retreatment.

Treatment guidelines for hematologic toxicities, and recommended actions regarding rovalpituzumab tesirine dosing, are outlined in Table 1.

Table 1. Guidelines for Managing Hematologic Toxicities

Toxicity	Recommended Action ^a for Rovalpituzumab Tesirine Doses		
Toxicity on Day 1 of Cycle			
Platelets < 75,000/μL	 Hold With resolution restart at original dose for next cycle If no resolution, reduce dosing 		

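### Operations Manual footnote b, read literally, removes every scheduled response assessment from Arm A subjects who qualify for retreatment because they progressed

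*Combined protocol and SAP*

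**What the plan says.** **Who may be retreated.** Protocol 5.1, criterion 2, gives two routes to Arm A retreatment. Both need at least stable disease on earlier treatment. The first then rests on a judgement that more treatment may help. The second needs a subject who has "experienced radiographic disease progression at least 12 weeks after last dose of rovalpituzumab tesirine per RECIST 1.1".

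**Which schedule applies.** Operations Manual 2.2 adds a screening visit in the 7 days before each retreatment period and then puts retreated subjects on the Arm B schedule in 2.3. A period has at most 2 cycles.

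**The limit.** The retreatment screening table in 2.2 has its own footnote b, under which response assessment and brain MRI are "to be performed only in subjects who have not yet experienced radiographic disease progression". The Post-Cycle and End of Treatment visits in 2.3 carry the same footnote: "Response assessment and brain MRI (if clinically indicated) to be performed only in subjects who have not yet experienced radiographic disease progression".

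**General rule.** Operations Manual 3.9 says that once a subject progresses or starts a new anticancer therapy, "disease/response assessment will consist of subsequent anticancer therapies and dates, date of progression (if not already captured), and survival status". It adds: "No subsequent radiography is required once disease progression has occurred".

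**Text pointing the other way.** Protocol Appendix D describes its tables as the required activities and ticks tumor imaging before each retreatment period, with no progression limit. Its Arm B imaging row has no such limit either. Protocol 3.1 undertakes to collect limited efficacy data on retreated patients, 3.2 to collect RECIST 1.1 response for each subject, and 7.4 to list tumor imaging for both arms.

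**The concern.** The condition that qualifies a subject under the second option is almost word for word the condition that footnote b uses to exclude a subject from response assessment. A site applying the footnote as written would give both retreatment doses with no scheduled scan to show whether the tumor responded, stayed stable or grew. A site working from Appendix D would scan. Two sites could therefore treat identical subjects differently, each with text to rely on.

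Two things are at stake. The first is the response record for retreated patients, the one group whose efficacy data the objective singles out. The second is smaller: the investigator would have no scheduled scan to inform the second dose. Protocol 2.2 reports shorter survival than with topotecan in one phase 3 population, so a dose given without current evidence of benefit is not a trivial matter, even though exposure is capped at 2 doses per period.

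**Working it through.** The plan has no figure to reproduce. It tests no hypothesis, fixes no sample size and summarizes no efficacy data. The check is a count of visits and a comparison of texts.

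**1. Scheduled assessments in one retreatment period.** Inputs: at most 2 cycles per period (Operations Manual 2.2); 6-week cycles (protocol 5.7). Length is 2 × 6 = 12 weeks, with 2 doses. The Post-Cycle visit applies only if another dose follows, so it occurs once, after cycle 1. End of Treatment follows the second dose.

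| Visit | Timing | Appendix D | Footnote b, no prior progression | Footnote b read literally, second-option subject |
|---|---|---|---|---|
| Retreatment screening | within 7 days before retreatment | 1 | 1 | 0 |
| Post-Cycle, cycle 1 | Days 35–42 | 1 | 1 | 0 |
| End of Treatment | 42 ± 3 days after last dose | 1 | 1 | 0 |
| Total | | 3 | 3 | 0 |
| After dosing starts | | 2 | 2 | 0 |

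**2. Is there a reset or exemption?** I looked in protocol 5.1 and Operations Manual 2.2, 2.3, 3.9 and 4.4. None says that progression status starts afresh at retreatment, and none exempts subjects still receiving drug. Appendix D lacks the limit but sends the reader to the Operations Manual for detail, where footnote b stands. Protocol 8.2 requires the study to follow both documents.

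**3. What imaging remains for a second-option subject?**
- The scan that documented progression. Criterion 2 implies it, but sets no limit on its age when retreatment starts.
- Brain imaging within 2 weeks before retreatment, for subjects with CNS metastases only (criterion 8).
- Diagnostic imaging before palliative radiation, if that is needed (Operations Manual 4.4).

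None of these is a scheduled measure of response to retreatment.

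**4. Against the stated collection.** Protocol 3.1, 3.2 and 7.4 call for response data on these subjects. With 0 scheduled assessments after the first retreatment dose, the listing would contain for them only what sites chose to scan.

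**5. Restart after isolated CNS progression.** Operations Manual 4.4 says "Investigational product may be restarted 1 week after the completion of local CNS disease-directed therapy", and "If more than 6 weeks have elapsed since the previous dose of study drug, the subject should undergo a radiographic tumor assessment". It does not mention the later scheduled assessments. If CNS-only progression counts as radiographic progression under footnote b, the assessments per 18-week Arm B block (3 cycles × 6 weeks, 2 doses) fall from 3 to 0. If it does not count, they stay at 3. The documents do not say which.

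**The case against.** **Intent to image is clear.** Appendix D, protocol 3.2 and 7.4, and the Post-Cycle note tying that visit to continued dosing all suggest that retreated subjects were meant to be scanned. A sensible site may read *not yet* as meaning since retreatment began. This stands as evidence of intent. It does not remove the conflict, because the footnote is printed on the retreatment screening table itself and Appendix D defers to the manual for detail.

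**The loss at screening is partly covered.** A progression scan must already exist, so the footnote at screening may simply avoid repeating it. This also stands in part: a reader might take 3 to 0 to mean that the subject has no imaging at all, and the documents do not support that. But with no limit on the age of that scan, it may be a poor baseline, and the two later assessments are still lost.

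**Section 3.9 adds little.** Its content matches survival follow-up, and not requiring a scan is not forbidding one. Agreed, though the sentence is not confined to subjects off drug.

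**A stronger reading concerns Arm B.** A reader might infer that Arm B subjects restarted after CNS-only progression could be dosed without a cycle cap while systemic progression went unseen. That needs CNS-only progression to count as progression for footnote b but not for the stopping rule in protocol 5.7. Section 4.4 treats it as a category of its own, attaches a tumor assessment to long gaps since the previous dose, and requires drug to stop if other sites have progressed. A site following 4.4 has little reason to think imaging has ended. Nor does 5.7 need amending: protocol 6.2 already lets drug be withheld for isolated CNS progression, and 4.4 says when it may restart.

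**Other safeguards.** The medical monitor should be consulted before retreatment, physical examinations continue each cycle, and the investigator can withdraw a subject.

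**Conclusion.** The conflict is real for Arm A subjects retreated under criterion 2, second option. Read literally, footnote b takes their scheduled response assessments from 3 to 0 per retreatment period. The firm loss is the 2 assessments after dosing starts. The third is the screening assessment, for which an older scan of unspecified age may stand in. Sites that follow Appendix D, or read the footnote as covering only new progression, lose nothing.

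Subjects retreated without prior progression, and Arm B subjects who stop drug at progression, are not affected. The CNS-restart question is an ambiguity worth one clarifying sentence; the documents do not show that those subjects would be dosed unmonitored.

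The number of subjects affected is not given and is probably small. No test, estimate or summary changes, because efficacy data are only listed. The case for acting is that the listing would otherwise lack, or hold unevenly across sites, response data that the protocol undertakes to collect. This rests on the text available for review, in which I found no rule on whether the protocol or the manual prevails.

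**What to change.** 1. In footnote b, at retreatment screening (2.2) and at Post-Cycle and End of Treatment (2.3), count only radiographic progression since the start of the current treatment or retreatment period.
2. State that the pre-retreatment scan is the new RECIST 1.1 baseline. The qualifying progression scan can serve if it falls within the 7-day screening window; otherwise a scan is taken at screening. Without this, continued scanning would not show response to retreatment.
3. In Operations Manual 3.9, limit the sentence on no further radiography to subjects no longer receiving study drug.
4. As a secondary clarification, say that subjects restarted under 4.4 after isolated CNS-only progression keep the scheduled assessments. Leave protocol 5.7 as it is.

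**Cost.** Wording only, with no new visit or procedure type. The downside is that routine scans already in Appendix D are kept in a probably small number of subjects: up to 3 per Arm A retreatment period, and one per 6-week cycle for any Arm B subject restarted after CNS-only progression.

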5 LOCAL LABS & IMAGING

- Disease/response assessment^b
- a. Visit can be a phone call for subjects who have already experienced disease progression.
- b. Response assessment and brain MRI (if clinically indicated) to be performed only in subjects who have not yet experienced radiographic disease progression.

NOTE Post-Treatment Follow-Up: For all subjects who discontinue study treatment for reasons other than disease progression, the first follow-up visit will occur at 6 weeks (± 1 week) after the last Response Assessment, then every 6 weeks (± 1 week) until 24 weeks after first dose of rovalpituzumab tesirine, then every 12 weeks (± 1 week) until disease progression or initiation of new anti-cancer therapy, whichever occurs first.

Survival Follow-Up: After disease progression or if subjects stop treatment and decline further study radiographic assessments prior to the endpoint of disease progression, subjects will be followed for subsequent anti-cancer therapies (dates and responses), as well as survival status, every 6 weeks* (± 1 week) until 24 weeks after first dose of rovalpituzumab tesirine, then every 12 weeks (± 2 weeks) until the endpoint of death, the subject becomes lost to follow-up or withdraws consent, or termination of the study by AbbVie, whichever occurs first (*or as requested by AbbVie). If the subject withdraws from study follow-up, the study staff may use a public information source (such as county records) to obtain information about survival status only, as appropriate per local regulations.

END OF STUDY VISIT

- Adverse event
- · Concomitant medications
- Disease/response assessment^b
- Survival status/Death (date and cause)
- Visit can be a phone call for subjects who have already experienced disease progression.
- b. Response assessment and brain MRI (if clinically indicated) to be performed only in subjects who have not yet experienced radiographic disease progression.

3 STUDY PROCEDURES

3.1 Subject Information and Informed Consent

The Investigator or his/her representative will explain the nature of the study to the subject and answer all questions regarding this study. Prior to any study-related screening procedures being performed on the subject or any medications being discontinued by the subject in order to participate in this study, the informed consent statement will be reviewed, signed, and dated by the subject, the person who administered the informed consent, and any other signatories according to local requirements. A copy of the signed informed consent will be given to the subject and the original will be placed in the subject's medical record. An entry must also be made in the subject's dated source documents to confirm that informed consent was obtained prior to any study-related procedures and that the subject received a signed copy.

Information regarding benefits for subjects and information regarding provisions for treating and/or compensating subjects who are harmed as a consequence of participation in the study can be found in the informed consent form.

